To demonstrate that  $\alpha 4\beta 2^*$  nAChRs are appropriate therapeutic targets in PD, it is necessary to study key pharmacokinetic-pharmacodynamic features of  $\alpha 4\beta 2^*$  nAChR *in the context of the degenerating, hypocholinergic PD brain*, a pathologic environment in which they may exhibit unique features. This *personalized medicine* approach focuses our studies on the subgroup of hypocholinergic PD subjects identified by **Project II** and the **Clinical Resource Core**. We will assess  $\alpha 4\beta 2^*$  nAChR features using PET imaging with the  $\alpha 4\beta 2^*$  nAChR ligand [F]flubatine, subacute administration of the  $\alpha 4\beta 2^*$  nAChR partial agonist varenicline (VCN), and laboratory measures of gait, balance, and attention. We will use [F]flubatine PET to assess VCN occupancy of brain  $\alpha 4\beta 2^*$  nAChRs. Using this PET data to select an appropriate VCN dose, we will perform a pharmacodynamic study with subacute VCN administration to determine if  $\alpha 4\beta 2^*$  nAChR stimulation improves laboratory measures of gait function, postural control, and attentional function in hypocholinergic PD subjects.

**Specific Aim 1:** To use [F]flubatine PET to assess VCN occupancy of brain  $\alpha 4\beta 2^*$  nAChRs after subacute VCN administration to the subgroup of PD subjects with cholinergic deficits in comparison with normal control subjects. **Hypothesis 1a:** Low dose, subacute VCN administration produces high  $\alpha 4\beta 2^*$  nAChR occupancy in PD subjects with cholinergic deficits.

**Hypothesis 1b:** Low dose, subacute VCN administration produces equivalent  $\alpha 4\beta 2^*$  nAChR occupancy in PD subjects with cholinergic deficits and normal control subjects.

**Specific Aim 2:** To assess the effects of pharmacologic  $\alpha 4\beta 2^*$  nAChR activation on laboratory measures of gait function and postural control in PD subjects with cholinergic deficits.

**Hypothesis 2:** Pharmacologic  $\alpha 4\beta 2^*$  nAChR activation in PD subjects with cholinergic deficits will improve laboratory measures of gait function and postural control.

**Specific Aim 3:** To assess the effects of pharmacologic  $\alpha 4\beta 2^*$  nAChR activation on a measure of attentional function (SAT; sustained attention test) in PD subjects with cholinergic deficits.

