We will investigate the possibility that regulation of  $\alpha 4\beta 2^*$  nAChRsmight be different in PD brain versus brains of normal individuals. We will investigate this possibility with a focused study of  $\alpha 4\beta 2^*$  nAChR receptor occupancy in a small group of normal subjects. Following the conclusion of receptor occupancy studies in hypocholinergic PD subjects, we will perform a more limited, parallel, dose-receptor occupancy study to determine if there are major differences in VCN receptor occupancy between PD and control subjects.

**Subject Selection**: PD subjects will be drawn from **Project II** subjects who have undergone [F]FEOBV imaging to identify cholinergic deficits.

We will study subjects with cortical innervation deficits below the 5th percentile cutoff of controls as defined previously (17). General inclusion and exclusion criteria are specified in the **Clinical** 

**Resource Core** and **Project II**. Current or previous (within last 6 months) use of any product or medication containing nicotinic agents, including use of tobacco products such as cigarettes, cigars, pipes, chewing tobacco, etc., e- cigarettes, OTC nicotine patches, chewing gum containing nicotine, or varenicline is an exclusion. While most data does not indicate that VCN causes suicidality or cardiovascular problems (73 -

81), we will exclude subjects with depression, active cardiovascular disease, history of seizures, or alcohol use disorders. (see **Human Subject Protection**).

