Figure 4: Timeline of SA1 Experiment

participants), to establish the required oral dose for **SA2** and **SA3** experiments. The results of the initial (0.25 mg/day maximum dose) study will be used to select the next dose point. If there is a substantial effect on [F]flubatine binding (>50% reduction), we will use the 0.25 mg bid maximum dose schedule for the next experiment. If the effect on [F]flubatine binding is <50% reduction, we will use 0.5 mg bid maximum dose schedule for the next experiment. Selection of the subsequent dose schedule will be based on the results of

the 0.5 mg bid maximum dose experiment. We will increment dose schedules until there is no additional reduction in [F]flubatine binding, i.e., remaining binding is non-specific binding, and the penultimate maximum dose defines our **SA2-SA3** study dose. Based on the work of Lotfipour et al., who found that a single oral 0.5

mg VCN dose produced ~100% receptor occupancy (70), we don't anticipate using the highest (1 mg po bid) dose schedule). We will measure plasma VCN levels at the time of the initial scan (Pharmacokinetics Core, U- M College of Pharmacy; see attached letter from [name], Core Director). These measurements are not for formal PK studies as VCN PK is well established, but rather to confirm study drug compliance. We aim to establish the lowest dose producing high ~100%) receptor occupancy and if we achieve this goal after studying 2 dose schedules (6 participants total), we will stop and proceed to **SA2** experiments.

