Following completion of the PD subject study experiment 1, we will perform a limited experiment to assess  $\alpha 4\beta 2^*$  nAChR occupancy in age-matched controls. Controls will receive VCN (no placebo) for 10 days. We will select a subset of the doses used for the PD subjects in experiment 1 to assess receptor occupancy in normal controls. Assuming we don't detect very high (>90%) occupancy with our initial dose (0.25 mg/day), we will expose controls to one of three different dosages of varenicline to construct a dose-occupancy relationship for comparison with the results in PD subjects. Based on the results of experiment 1, experiment 2 will include the following dosages

with a goal of 3 patients per cohort: .25mg QD, .25mg BID and .5mg BID. All procedures will be identical to experiment 1. Control subjects will be drawn from the normal control pool characterized concurrently in the Clinical Core of the Udall project, much as the PD subjects are drawn from the pool of PD subjects. Control subjects will also be recruited from the UM Health Research website if needed. We anticipate studying 9 subjects, 3 at each dosage point. To adjust for potential dropouts, we will budget 12 control subjects.

Potential Problems and Alternatives: The results of Loftipour et al. suggest that low doses will produce high  $\alpha 4\beta 2^*$  nAChR occupancy (70). Commercially available VCN pills are small and division beyond bisection is likely to be inaccurate. 0.25 mg/day is the lowest feasible dose and if we find this dose produces high per cent receptor occupancy, no further testing will be necessary. VCN tolerability may be a problem as this agent has not been tried specifically in PD subjects previously. To avoid any problems, we are starting with low doses and using an incrementing schedule. Nausea was infrequent in a recent trial in AD which used significantly higher doses (89). If tolerability is an issue, then we will alter the incrementing schedule to more gradually "ramp" up to the desired dose.

**Specific Aim 2:** To assess the effects of pharmacologic  $\alpha 4\beta 2^*$  nAChR activation on laboratory measures of gait function and postural control in PD subjects with cholinergic deficits.

*Rationale and Predictions:* The central hypothesis of this project is that deficient activation of  $\alpha 4\beta 2^*$  nAChRs consequent to the degeneration of cholinergic projections causes balance and gait abnormalities in PD.

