#### Inclusion Criteria:

- 1. PD diagnosis will be based on the United Kingdom Parkinson's Disease Society Brain Bank Research Center (UKPDSBRC) clinical diagnostic criteria. We will enrich the cohort using the following strategies: recruiting subjects at modified Hoehn and Yahr stages 2 or higher (from data collected in a medication "OFF" state in UDALL project 2), recruiting subjects with a duration of motor disease 5 years or longer, recruiting subjects that are age >65 years, or recruiting subjects with the PIGD phenotype. Duration of motor disease will be defined as the time between onset of motor symptoms and time of entry into the study. The PIGD phenotype is defined as described previously. PD subjects with defined cholinergic deficits will be recruited as described in **Project II**. PD subjects will have cortical cholinergic deficits based on 5th percentile cutoff of the normal controls as defined previously.
- 2. PD Patients with stable dopaminergic replacement therapy for 3 months prior to enrollment and expected to maintain stable dopaminergic therapy for duration of study participation.

3. Normal healthy control individuals age 45 years and older without any history of neurological disease.

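### Aim 1 compares Parkinson's disease (PD) and control occupancy by nominal dose and leaves the plasma varenicline level at the scan as a compliance check; a concentration-based comparison should sit beside it

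*Protocol*

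**What the plan says.** Hypothesis 1b (Protocol, Specific Aims) is worded by dose: "Low dose, subacute VCN administration produces equivalent" occupancy in PD subjects with cholinergic deficits and in normal controls. No equivalence margin is given. The Overall Rationale and Organization section motivates the control experiment by asking whether receptor regulation differs in PD brain, and describes a dose-occupancy study "to determine if there are major differences in VCN receptor occupancy between PD and control subjects".

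Under Specific Aim 1, Procedures, controls are studied "with a goal of 3 patients per cohort: .25mg QD, .25mg BID and .5mg BID", to "construct a dose-occupancy relationship for comparison with the results in PD subjects". Three dose levels are planned if the lowest dose does not give occupancy above 90%. The PD part anticipates three dose points with three participants each.

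On exposure, the same Procedures text says "We will measure plasma VCN levels at the time of the initial scan", and then: "These measurements are not for formal PK studies as VCN PK is well established, but rather to confirm study drug compliance". For controls, "All procedures will be identical to experiment 1", so both groups should have a level paired with the on-drug scan. Nothing in the protocol or SAP relates occupancy to that level. The SAP (section 5) says only that the occupancy sample size was logistical, and it contains no occupancy analysis.

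**The concern.** At a fixed oral dose, a higher plasma concentration raises occupancy just as a higher receptor affinity would. A comparison by dose cannot tell the two apart, and an exposure difference in the opposite direction can conceal a real receptor difference.

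The documents leave room for such differences. The background on nicotinic partial agonists describes varenicline as cleared mainly by the kidney. This protocol's inclusion and exclusion criteria list no renal function criterion, and no renal matching is described. (General criteria are said to be set out in the Clinical Resource Core and Project II documents, which are not part of this set.) The on-drug scan is fixed only as the afternoon following a morning dose, without a set interval. Even with no systematic difference, three people against three will differ in exposure by chance.

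At stake is the reading of Hypothesis 1b: whether a gap between PD and controls, or its absence, says anything about receptors.

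**Working it through.** There is no power or precision figure for this comparison to reproduce. The cohort arithmetic is consistent: 3 doses × 3 = 9 controls, with 12 budgeted (9/12 = 0.75, an implied allowance of 25%).

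**Model and inputs.** One-site binding: occupancy = R/(1 + R), with R = concentration/EC50, where EC50 is the concentration giving half-saturation. PD and controls have the same EC50, so there is no receptor difference. From the protocol: three people per dose per group. Assumed, because the documents give neither: the group exposure ratio k, and the between-person coefficient of variation (CV) of exposure.

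**Step 1: a systematic exposure difference.** The shift is kR/(1 + kR) − R/(1 + R). At 50% occupancy R = 1, and with k = 1.25 this is 1.25/2.25 − 0.50 = 5.6 points. At 90% R = 9, giving 11.25/12.25 − 0.90 = 1.8 points.

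| True occupancy | k = 1.25 | k = 1.5 | k = 2 |
|---|---|---|---|
| 50% | +5.6 | +10.0 | +16.7 |
| 80% | +3.3 | +5.7 | +8.9 |
| 90% | +1.8 | +3.1 | +4.7 |
| 95% | +1.0 | +1.6 | +2.4 |

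**Step 2: chance alone, three against three at one dose.** With s = √ln(1 + CV²), the log exposure ratio has standard error s√(2/3), and its 95% range is exp(±1.96 × s√(2/3)). For CV 30%, s = 0.294, the standard error is 0.240, and the range is 0.63 to 1.60. The occupancy columns come from 100,000 simulated comparisons without PET measurement error.

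| CV | 95% range of exposure ratio | Points at 50% | Points at 80% | Points at 95% |
|---|---|---|---|---|
| 20% | 0.73–1.37 | ±7.8 | ±5.1 | ±1.5 |
| 30% | 0.63–1.60 | ±11.5 | ±7.6 | ±2.4 |
| 40% | 0.54–1.85 | ±14.9 | ±10.0 | ±3.2 |
| 50% | 0.47–2.13 | ±17.9 | ±12.4 | ±4.1 |

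Pooling three doses (nine against nine) replaces √(2/3) by √(2/9). At CV 30% the range narrows to exp(±1.96 × 0.138) = 0.76 to 1.31. That reduces chance imbalance but does nothing about a systematic difference.

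**Step 3: effect on a fitted curve.** Fitted by dose, an exposure ratio of 1.3 with identical receptors appears as an EC50 ratio of 1/1.3 = 0.77, a false difference of about 23%. Simulated fits of the 3 × 3 × 2 design gave 22–24% by dose and about none by plasma level. They assumed exposure CV 35%, occupancy measurement SD 3 points, and 80–95% occupancy at 1 mg/day. With 20% random error added to the plasma level, the remaining bias was under 2%.

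**Step 4: precision.** In the same simulations with equal group exposure, the SD of the log EC50 ratio was:

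| Exposure CV | Error in plasma level | By dose | By plasma |
|---|---|---|---|
| 35% | none | about 0.18–0.26 | 0.07–0.14 |
| 35% | 20% | about 0.18–0.26 | 0.12–0.19 |
| 35% | 35% | 0.17–0.26 | 0.18–0.27 |
| 20% | 35% | 0.12–0.19 | 0.18–0.28 |

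With both at 20% there was no gain. The benefit for bias therefore holds more widely than any benefit for precision.

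**The case against.** The strongest reply is that the by-dose comparison answers the hypothesis as written. Hypothesis 1b concerns occupancy after low-dose administration, and the rationale asks only about major differences. That stands, and it is why the concentration analysis belongs beside the by-dose comparison and should not replace it. An EC50 ratio is also a different quantity. It does not capture receptor number, so it would not settle every meaning of altered regulation.

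A reader might infer an age confounder, since eligibility asks for "Normal healthy control individuals age 45 years and older" while the risk-protection text speaks of participants in their seventies and eighties. The documents do not support that step. Specific Aim 1 calls the controls age-matched and states that varenicline pharmacokinetics do not vary with age, and the remark about older participants refers to similar ongoing studies. Those statements do not deal with renal function, adherence or time from dose to scan, although nothing in the documents shows that renal function differs between the groups.

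A reader might also expect the plasma analysis to be more precise. Step 4 shows that this depends on how well a single level measures exposure.

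Finally, the protocol expects high occupancy at low doses. At 90–95% a 1.3-fold exposure ratio moves occupancy by only 2.1 to 1.1 points (11.7/12.7 − 0.90 and 24.7/25.7 − 0.95). This limits the size of the point. However, the three-dose control experiment is planned for the case where the lowest dose does not exceed 90%, and near saturation the comparison says little about receptors in any case.

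**Conclusion.** The point holds as a cheap improvement. The plan compares groups by dose, collects the exposure measure that would help interpret the comparison, and assigns it only to checking compliance. Under a one-site model with assumed exposure ratios of 1.25 to 2, identical receptors would appear to differ by about 6 to 17 points at 50% occupancy, 3 to 9 at 80%, 2 to 5 at 90% and 1 to 2 at 95%. It is material mainly below about 90%.

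It would go too far to say that the by-dose comparison is invalid, or that no gap could ever be attributed to receptors. The levels will exist, and the disclaimer of formal pharmacokinetic work does not bar plotting occupancy against them. Nor does the point reach the rest of the trial: the dose for Aims 2 and 3 is chosen from PD data alone, and the crossover endpoints do not use the control comparison. With about nine people per group and no equivalence margin, the result remains descriptive under either analysis.

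**What to change.** Keep the by-dose table and comparison for Hypothesis 1b. Pre-specify beside it a joint analysis of all PD and control participants: occupancy = C/(C + EC50), with C the individual plasma varenicline level at the on-drug scan and one group term on log EC50. Report the PD/control EC50 ratio with its confidence interval, a plot of individual values by group, plasma levels by group and dose, and the time from last dose to scan. State that the analysis is descriptive.

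The cost is analysis text and a record of dose-to-scan time, because the blood samples and assays are already planned. There are two limits to state in the plan. A single level measures exposure with error, so bias from a group exposure difference is reduced but better precision is not assured. If every dose nearly saturates the receptors, EC50 will be poorly estimated, and a wide interval should be read that way.

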Analysis Method. For all aims, we will conduct exploratory analyses to examine the distributions of outcomes under each treatment, as well as individual and mean profiles over time. Graphical approaches such as boxplots and scatterplots with linear or non-linear (e.g., loess) methods will be used, allowing identification of outliers, linearity, and correlation of measurements within person and across time. If outcome data do not appear normally distributed, transformations will be employed. Because participants' outcomes will measured at more than one time point per person, our analyses will be based on linear mixed effects models (108-110). We expect no carryover since treatments will be spaced three weeks apart. Tests to compare treatments will be based on Wald and chi-squared tests based on maximum likelihood or restricted maximum likelihood methods. Alternative covariance structures (other than compound symmetry) will also be explored and model fit examined using the Akaike Information Criteria (AIC).

Potential Problems and Alternatives: All measures proposed for this experiment are well established in the University of Michigan Functional Neuroimaging, Cognitive and Mobility Laboratory and the **Clinical Resource Core**. The major foreseeable difficulties are subject recruitment and retention. We've had considerable success recruiting and retaining subjects in protocols involving up to 4 PET studies, serial evaluations, long-term follow-up (months to years), and subject clinical-psychometric-gait & balance evaluations as intensive as those proposed. We budget a 10% drop out rate in this study, which is typical of our experience in prior prospective studies and identical to the dropout rate in the recent AD study (89). A related concern would be unexpected difficulty with VCN tolerability, leading to excessive dropouts. The goal of the SA1 experiments is to find the lowest dose providing high  $\alpha 4\beta 2^*$  nAChR occupancy, which provides protection against this possibility. In the recent AD study, VCN was tolerated well at higher doses than we expect to employ. If tolerability is a problem, we would use a slower dose escalation regimen.

It is possible that there will be differential effects of VCN on gait speed and postural control. We will be drawing these subjects from **Project II**, where all participants will receive anatomically resolute [F]FEOBV imaging. As discussed in **Project II**, there may be correlates between specific pathway deficits, such as BF projection versus PPN projection degeneration, or even more specific pathway changes such as PPN to cerebellar vermis projection deficits, and specific gait or postural control measures (see **Project II** Preliminary

Data). We will have a rich dataset to examine these possibilities, including not only imaging data but also the considerable gait and balance data generated by the Mobility Laboratory system for exploratory analyses. It is possible that VCN will have no effect on gait, balance, or cognition in these subjects. This would be disappointing but important as it would steer the field towards other types of cholinergic receptors as therapeutic targets. Comparison of these results with parallel **Project I** experiments will also be important for evaluating the novel model developed in that Project.

**Specific Aim 3:** To assess the effects of pharmacologic α4β2\* nAChR activation on a measure of attentional function (SAT; sustained attention test) in PD subjects with cholinergic deficits.

[figure not shown]
Rationale and Predictions: Our preclinical work with a novel rodent model of cholinergic-dopaminergic gait deficits indicates that diminished attentional function following loss of corticopetal BF afferents is a key mediator of the effects of cholinergic system degeneration on gait and balance (**Overview**; **Project 1**). A large body of prior research indicates attentional function impairments contribute significantly to impaired gait and postural control, including falls, in normal elderly and PD patients (33-39). In a recent large prospective study, for example, attentional function deficits predicted falls in older adults (39). [name] extensive prior work

indicates that  $\alpha 4\beta 2^*$  nAChRs are crucial actors in cholinergic modulation of attention (**Project 1**) (42-46). Consistent with this work, our preliminary preclinical data suggests that stimulation of  $\alpha 4\beta 2^*$  nAChRs improves gait and balance in the novel dual lesion model (**Project 1**). These combined results lead to an important prediction: subacute  $\alpha 4\beta 2^*$  nAChR administration to hypocholinergic PD subjects will improve attentional performance and improved attentional performance will correlate with improved gait and postural control induced by  $\alpha 4\beta 2^*$  nAChR stimulation. Evaluating this prediction is important for assessing the mechanisms by which cholinergic projection system degeneration impairs gait and balance and is important also for assessing the validity of the novel rodent model presented in **Project 1**.

*Preliminary Data:* [name] group developed a robust test of attentional function, the Sustained Attention Test (SAT), for use in rodent experiments, and subsequently adapted and validated the SAT for use in humans (**Project 1**) (111-113). Briefly the SAT consists of a randomized sequence of cued and non-cued (or signal and nonsignal) trials. Responses are hits and misses, and correct rejections and false alarms, respectively. Hits and correct rejections are rewarded. SAT performance reflects frontal cortical cholinergic signaling through  $\alpha 4\beta 2^*$  nAChRs. We evaluated a particularly

relevant version of the SAT including a distractor component (dSAT), in PD subjects who had previously undergone [C]PMP imaging to assess cholinergic projection systems integrity. There was considerable variation in dSAT performance, which was a linear function of cortical cholinergic terminal integrity

(**Figure 6**). These results indicate that dSAT performance in PD directly reflects cortical cholinergic signaling, likely mediated by  $\alpha 4\beta 2^{\circ}$  nAChRs.

*Procedures:* This experiment will be conducted in parallel with those for SA2. Attention will be evaluated with the dSAT at all evaluation points in the double-blind crossover design VCN intervention study described above. We will correlate dSAT changes in response to VCN with gait speed and postural control changes in response to VCN. The sample size is determined from the goals of **SA2**. With this sample size, an effect size of 0.4 can be detected with at least

80% power and a two-sided Type I error of 0.05 assuming a within-subject correlation of 0.69. Similar statistical methods as those used for SA2 will be employed to test the impact of VCN on dSAT. An exploratory analysis will be conducted to examine medication of treatment effects on gait and other postural outcomes by dSAT. In the presence of a treatment effect, a variable is declared a mediator if it complies with three things: it is affected by the treatment, it predicts the endpoint of interest, and the treatment effect is attenuated when the potential mediating factor is adjusted for. Mediation analysis will be conducted by including mediating factors in the mixed model regression analysis outlined above. Structural equation models will be used to estimate the direct effect of VCN and the indirect effects of the VCN due to mediators, as has been recommended for intervention studies of disease prevention (114,115).

Potential Problems and Alternatives: All procedures, including the dSAT, are well established in our center. Most of the potential problems are discussed above (**SA2** Potential Problems and Alternatives). Our prediction is that improved dSAT performance will correlate with improved gait speed and postural control measures. There may be dissociations between results of dSAT testing and gait speed-postural control outcome measures. Attentional performance may improve but not gait speed and postural control. Gait speed and postural control may improve without commensurate improvements in dSAT performance. These outcomes would be important for evaluating our understanding of how cholinergic deficits degrade gait and postural control. Lack of correlation would direct future research away from attentional mechanisms and towards alternative mechanisms, such as PPN projection roles in sensorimotor integration. We will have

[F]FEOBV data on cholinergic projection systems integrity for all these subjects and secondary analyses looking at specific functional deficits and specific pathway changes may be revealing. Whether or not dSAT

performance response correlates with improvements in gait speed and postural control measures is also important for evaluating the validity of the dual lesion model. It is crucial to know the limitations of this interesting model prior to using it extensively for preclinical evaluations of potential therapies.

